9.1 DSMC Auditing

In addition to monitoring, the DSMC oversees an internal auditing process to ensure subject safety and data quality. All cancer-related clinical trials active at the SCC are eligible for audit; however, priority is placed on those clinical trials that are not monitored or audited by an outside entity. If an external entity conducts an audit of a clinical trial at the SCC, then the findings of that audit are reported to the DSMC, either through the formal audit report provided by the external auditing entity, if available, or from the PI, who will report any findings communicated during the audit process.

9.2 Data Handling and Record Keeping

9.2.1 Data Quality Assurance

Stephenson Cancer Center (SCC) will be responsible for clinical monitoring of all data for this study.

9.2.2 Electronic Database and Case Report Forms

The Principal Investigator and designated team will develop a study-specific electronic database in REDCap and study-specific case report forms for study data entry. All study data will be recorded into the REDCap database sponsored by OU-SCC and stored in a 21 CFR 11-compliant database. Appendix A and B will be paper based and later scanned into REDCAP. Only the Investigator and assigned research staff will have access to the study data. All case report forms will be available to Sponsor, IRB or regulatory authorities in event of an audit or inspection.

9.2.3 Data Disclosure and Subject Confidentiality

Subject medical information obtained as a result of this study is considered confidential. Disclosure to third parties other than those noted below is prohibited. All reports and communications relating to subjects in this study will identify each subject only by their initials and number. Medical information resulting from a subject's participation in this study may be given to the subject's personal physician or to the appropriate medical personnel responsible for the subject's welfare. Data generated as a result of this study are to be available for inspection on request by FDA or other government regulatory agency inspectors, the SCC clinical trial office auditors and monitors, Office of Compliance, and the Institutional Review Board (IRB).

All evaluation forms, reports, and other records that leave the site will be identified by a coded number, and/or initials to maintain subject confidentiality. All study records will be kept in a locked file cabinet or other secured area. All computer entry and networking programs will be identifiable only by coded numbers and/or initials. Subject personal medical information may be reviewed by representatives of the Sponsor, IRB, or regulatory authorities in the course of monitoring the progress of the clinical trial. Every reasonable effort will be made to maintain such information as confidential.

9.2.4 Record Retention

In accordance with 21 CFR 812.140, the Sponsor and Investigator will retain all research documents relating to the participation in the clinical trial. These documents must be retained for a period of two years after the date on which the investigation is terminated or completed, or the date that the records are no longer required for purposes of supporting a premarket approval application, a notice of completion of a product development protocol, a humanitarian device exemption application, a premarket notification submission, or a request for De Novo classification.

If the transfer of records custody during the retention period is accepted by any other person, notice of transfer must be given to FDA not later than 10 working days after transfer occurs.

9.3 Study Monitoring

All aspects of the study will be carefully monitored at periodic intervals throughout the study per FDA/ICH "Guidance for Industry – E6 Good Clinical Practice: Consolidated Guidance" dated April 1996. All Case Report Forms (CRFs) will be up to 100% source verified against corresponding source documentation (e.g., office and clinical laboratory records) for each subject. The monitoring visits provide the PI with the opportunity to evaluate the progress of the study, to verify appropriate consent form procedures, and to verify the accuracy and completeness of CRFs, to resolve any inconsistencies in the study records and to assure that all protocol requirements, applicable FDA regulations, other requirements, and Investigator's obligations are being fulfilled.

Furthermore, this study will fall under the purview of the Stephenson Cancer Center Data Safety Monitoring Committee (DSMC).

10.0 Statistical Considerations

10.1 Analysis of Primary Objective

10.1.1 The primary objectives are to estimate the rate of adverse events and measure the skin temperature change following MSOT imaging both pre- and post-surgery. The adverse events will be estimated by grade, type and relatedness. The first analysis will pool all grade 3 unexpected events that are possibly, probably or definitely related to MSOT together and then construct a 95% exact Clopper-Pearson binomial confidence interval for this estimate. Additionally, measurement of skin temperature will be evaluated where skin temperature greater than 44°C will be recorded¹³. A 95% exact Clopper-Pearson binomial confidence interval for the evaluation of skin temperature will be conducted

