10.3 Power and Sample Size

10.3.1 We will initially accrue 10 patients for safety analysis regarding the use of the MSOT device pre- and post-surgery. If there are no grade III-V AEs observed in the patients as defined in CTCAE v5.0 per [Section 8.2](#), we will submit an IDE supplement to request an enrollment expansion for an additional 40 patients, for a total of 50 patients. Up to an additional 55 patients will be accrued (to account for patient dropouts) to enroll 40 patients. Thus, a total of 50 patients will be enrolled and scanned (10 patients in the initial analysis and 40 patients following the interim analysis) in order to gather sufficient data to evaluate the proportion of patients with adverse events that may be associated with the MSOT approach. The MSOT approach is not expected to be related to any adverse events except for a possible slight, reversible reddening and temperature increase of sensitive skin. Nevertheless, this study will allow us to estimate the proportion of unexpected adverse events of grade 3 or higher that are possibly, probably, or definitely related to the MSOT approach. With 50 patients, the upper bound of a 95% Clopper-Pearson exact confidence interval will be less than 20% if the observed rate of adverse events is 8% or less (4 out of 50 or less). We expect that the actual value will be 0 out of 50 – and if this is observed the upper bound of this confidence interval will be 7.1% which would provide a useful upper bound for the potential of adverse events.

The study will be terminated early, after 45 patients in total are enrolled and scanned, if 3 or fewer AEs are observed in the patients scanned by the MSOT device, based on the assumption that the upper limit of the 95% Clopper-Pearson exact confidence interval will be less than 20%. The upper limit of the 95% Clopper-Pearson exact confidence interval will be 7.9%, 11.7%, 15.1% or 18.3% respectively for 0, 1, 2, or 3 observed AEs.

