10.3.2 **Interim analysis:** This study will initially accrue 10 patients to identify any potential grade III or IV AEs defined in CTCAE v5.0 per [Section 8.2](#). As yet, no study using MSOT in over 600 patients has observed any grade III or IV AEs^{2,3,14,15}. An interim analysis will be conducted after the first 10 patients. If there are no grade III or IV AEs observed in the patients, we will submit an IDE supplement with preliminary safety data, to request an enrollment expansion to 50 patients. If any grade V AEs occur during the investigation, the FDA will be notified immediately and the study halted for further accrual until discussed with FDA.

10.4 **Estimated Accrual Rate**

10.4.1 The estimated accrual rate is 10-20 patients per month after the initial accrual of 10 patients.

10.5 **Estimated Study Length**

10.5.1 Subjects will be actively enrolled only for the duration of pre-op through surgical recovery, and until post-op discharge unless any study-related adverse event occurs. Medical record review will occur up to 6 months to allow for follow-up pathology assessments to be gathered and provide information to allow for analyses to be performed as previously described.

11.0 **ETHICAL AND REGULATORY CONSIDERATIONS**

11.1 **Ethical Conduct of the Study**

The study will be conducted in full conformance with the ICH E6 guideline for Good Clinical Practice and the principles of the Declaration of Helsinki in addition to the requirements of the ICH E2A guidelines. This study will also comply with U.S. FDA regulations under a U.S. Investigational Device Exemption (IDE) application in addition to local, state, and federal laws.

11.2 **Informed Consent**

The informed consent document will be in compliance with ICH GCP, local regulatory requirements, and legal requirements. The informed consent document used in this study, and any changes made during the course of the study, will be prospectively approved by the IRB of record.

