Appendix A – Imaging and Tissue Data Collection Form

Study Number: OU-SCC-MSOT PID: 0 1 - _____

Investigator: [name] Surgery Date: ____/____/____

1) Tumor or Lymph Node Assessments:

a) Target tissue

Tumor

Lymph Node

b) Standard of care method of imaging

MRI _____ tumor amount

PET _____ tumor amount

CT _____ tumor amount

Other: _____ tumor amount

c) Did patient receive neoadjuvant therapy?

Yes

No

d) MSOT Image acquired?

Yes

No

e) Was an indicator dye used during surgery?

Yes

[figure not shown]
No

f) If an indicator dye used during surgery, please indicate which dye.

Isosulfan Blue IC Green

2) Location of Imaging

a) Please circle the location of the imaging (below) and provide further description as necessary

[https://anatomyclass123.com /](https://anatomyclass123.com/)

b) Erythema post-MSOT Imaging (RTOG)

i. Time after imaging: (hr: min) _____

ii. Grade (RTOG)

- 0 No erythema present
- 1 Follicular, faint or dull erythema, epilation, dry desquamation, decreased sweating
- 2 Tender or bright erythema, patchy moist desquamation, moderate edema
- 3 Confluent, moist desquamations other than skin folds, pitting, edema
- 4 Ulceration, hemorrhage, necrosis

3) Clinical Pathology Assessment

a) Date or diagnosis (month / year):

b) Positive tumor tissue:

Yes No
 c) For Pancreatic melanoma breast HNSCC ovarian (check one) indicate stage at diagnosis (**TNM classification**):

Tx T0 Tis T1 T2 T3 T4
 Nx N0 N1 N2 N3
 Mx M0 M1

d) Tumor subtype (if applicable) _____

4) Skin temperatures

Pre-Surgery MSOT imaging			
Pre-imaging Skin Temperature (°C)		Time	
Post-imaging Skin Temperature (°C)		Time	

Post-Surgery MSOT imaging			
Pre-imaging Skin Temperature (°C)		Time	
Post-imaging Skin Temperature (°C)		Time	

5) Patient Monitoring (*)please note that patients must be monitored daily for adverse events until discharge). Please answer yes or no if Erythema at grade III or higher or change in skin pigmentation occurs.**

Yes No

_____ Post surgery	_____ 8 day
_____ 1 day	_____ 9 day
_____ 2 day	_____ 10 day
_____ 3 day	_____ 11 day
_____ 4 day	_____ 12 day
_____ 5 day	_____ 13 day
_____ 6 day	_____ 14 day
_____ 7 day	_____ 15 day

Discharge date: _____

6) Adverse event. Please answer yes or no if Erythema at grade III or higher or change in skin pigmentation occurs.

Yes No

If yes, please fill out details below:

_____ Erythema _____ Time _____ Date

_____ Changes in skin pigmentation _____ Date

7) MSOT Scan Times:

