- ii. Identification of tumor and/or lymph nodes based upon either Isosulfan Blue or IC Green dye

3. Design information

a. General statistical considerations

This IDE FDA approved study will involve the interaction with patients that are scheduled for routine standard of care surgery. It will be a single-arm study that is designed to provide safety information regarding the use of the Acuity MSOT device in the clinical setting and the ability of MSOT imaging data to correlate with clinical findings identified via pathology.

b. Sample Size and Power

Study will initially accrue 10 patients for safety analysis regarding the use of the MSOT device pre- and post-surgery. If there are no grade III-V AEs observed in the patients as defined in CTCAE v5.0 per Section 8.2, we will submit an IDE supplement to request an enrollment expansion for an additional 40 patients, for a total of 50 patients. Up to an additional 55 patients will be accrued (to account for patient dropouts) to enroll 40 patients.

4. Study Populations

Inclusion and exclusion criteria are sometimes modified during the duration of the protocol. Before beginning analysis, the statistical team will review the criteria in the SAP to confirm it is up to date with the current criteria.

a. Inclusion Criteria

- i. Patients with an identified solid tumor, i.e. breast (Stage I-IV), melanoma (Stage I-IV), HNSCC (Stage I-III), pancreatic (Stage I-III), ovarian (Stage I-IV) that is scheduled for surgical removal of the tumor and completed standard imaging prior to surgery
- ii. Have acceptable hematologic status [total hemoglobin (tHb) \geq 10 mg/dL]
- iii. Patients \geq 18 yrs of age
- iv. Patient provided a signed and dated informed consent
- v. Willing to comply with study procedures and be available for the duration of the study
- vi. Ability to understand and the willingness to sign an IRB-approved informed consent document.

b. Exclusion Criteria

- i. Patients with central nervous system tumors
- ii. Patients with a tattoo over the surgical site
- iii. Pregnant women
- iv. Women who are breastfeeding
- v. Systemic or local infection
- vi. Any systemic anomaly during the pre-op assessment preventing patient participation in the study
- vii. Any febrile illness that precludes or delays participation preoperatively
- viii. Anything that would put the participant at increased risk or preclude compliance with the study

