- ix. Patients with Stage IV pancreatic cancer, Stage IV HNSCC are not surgical candidates and therefore excluded from this study

5. Analysis Populations

- **Safety population:** All subjects who received MSOT readings will be included in the overall safety analysis, with toxicities graded according to NCI CTCAE v5.0. This is primarily a safety analysis study.

6. Summary of Study Population

a. Patient Disposition

- i. Descriptive statistics on the demographics and presenting features will be calculated. Proportions will be calculated for categorical variables and medians with the minimum and maximum will be calculated for continuous variables.

7. Safety Analyses

a. Adverse Events

- i. The severity of the AE will be graded by the Investigator using the NCI CTCAE, version 5.0.
- ii. The adverse events will be estimated by grade, type and relatedness. The first analysis will pool all grade 3 unexpected events that are possibly, probably or

definitely related to MSOT together and then construct a 95% exact Clopper-Pearson binomial confidence interval for this estimate.

b. Temperature Analysis

- i. Measurement of skin temperature will be evaluated where skin temperature greater than 44°C will be recorded and a 95% exact Clopper-Pearson binomial confidence interval constructed.

c. Secondary Analysis

- i. Tumor positivity from pathology reports and MSOT readings will be compared and Pearson correlation coefficient created.
- ii. Deoxy- and oxy-genation levels will be compared to non-tumor values from the same patient. Paired t-tests will be used to compare the values and a Wilcoxon Signed Rank test performed. Median and interquartile range will be reported.

8. Handling of Missing Data

Every effort will be made to collect information at all defined visits including at early withdrawal or dropout. Reasons for missing data will be summarized. However, there will be no imputation of missing data.

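### The pooled primary safety rate is defined on grade 3 events in Protocol 10.1.1 and SAP 7.a.ii, but on grade 3 or higher in Protocol 10.3.1

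*Protocol*

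**What the plan says.** Protocol 10.1.1 plans to estimate adverse events by grade, type and relatedness. It then sets out a pooled analysis with a 95% exact Clopper-Pearson interval: "The first analysis will pool all grade 3 unexpected events that are possibly, probably or definitely related to MSOT together". SAP 7.a.ii uses the same wording, beginning "The first analysis will pool all grade 3 unexpected events that are possibly, probably or". Neither text adds anything about higher grades.

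Protocol 10.3.1 describes the target of estimation as the "proportion of unexpected adverse events of grade 3 or higher that are possibly, probably, or definitely related to the MSOT approach". It then gives the precision expected with 50 patients: the upper limit "will be less than 20% if the observed rate of adverse events is 8% or less (4 out of 50 or less", and 7.1% if no patient has such an event.

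SAP 3.b takes over the start of 10.3.1, including the expansion check ("If there are no grade III-V AEs observed in the patients as defined in CTCAE v5.0"), but stops before the sentence on grade 3 or higher and before the bounds. SAP 5 defines the safety population: "All subjects who received MSOT readings will be included in the overall safety analysis".

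**The concern.** The two definitions agree on expectedness and relatedness and differ on grade. An analyst programming from the SAP alone finds only grade 3 for this rate. If the text is followed as written, the most severe related events are left out of the pooled estimate meant to bound serious harm from the device. The reported rate and its upper limit would then be too low, and would not be the quantity that 10.3.1 says the study estimates. The gap appears only if a related, unexpected grade 4 or 5 event occurs, which is when the pooled rate matters most.

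**Working it through.** **1. The definitions side by side**

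| Element | Protocol 10.1.1 and SAP 7.a.ii | Protocol 10.3.1 |
|---|---|---|
| Expectedness | unexpected | unexpected |
| Relatedness | possible, probable or definite | possible, probable or definite |
| Grade | 3 | 3 or higher |
| What is counted | events | patients, as implied by 4 out of 50 |
| Interval | 95% Clopper-Pearson | 95% Clopper-Pearson |

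**2. Does any other text settle the grade?**

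- The expansion check in Protocol 10.3.1 and SAP 3.b covers grades III to V, but it is a separate rule about enlarging the study.
- Appendix A, item 6, asks: "Please answer yes or no if Erythema at grade III or higher or change in skin pigmentation occurs". This concerns skin findings only, and the erythema scale printed on that form is RTOG, not CTCAE.
- Both show that the documents write out a range when they mean one. Neither says that grade 3 in 10.1.1 includes grades 4 and 5.

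**3. Reproducing the plan's figures**

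For x patients with an event out of n, the two-sided 95% limits are:

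- lower = Beta quantile(0.025; x, n − x + 1), or 0 when x = 0
- upper = Beta quantile(0.975; x + 1, n − x)

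With x = 0 and n = 50 the upper limit reduces to 1 − 0.025^(1/50) = 7.11%, which matches the stated 7.1%. With x = 4 and n = 50 it is 19.23%, which agrees with the statement that it lies below 20%. These figures depend only on x and n, so they hold under either grade definition.

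**4. What the wording can change**

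The documents give no expected number of grade 4-5 events. The counts below are assumed, all events are taken to be unexpected and related, and each patient has at most one.

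| Assumed patients, n = 50 | As written | Grade 3 or higher |
|---|---|---|
| none at grade 3, none at grade 4-5 | 0/50: 0 to 7.1% | 0/50: 0 to 7.1% |
| none at grade 3, one at grade 4-5 | 0/50: 0 to 7.1% | 1/50: 0.05% to 10.6% |
| four at grade 3, one other at grade 4-5 | 4/50: 2.2% to 19.2% | 5/50: 3.3% to 21.8% |

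The second row is the more realistic illustration. The third shows the effect near the 20% figure in 10.3.1.

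**The case against.** The strongest reply is that the intent is plain. Section 10.3.1 states the wider definition, and a statistician with both documents open would very likely use it. That stands, and it makes this a wording conflict rather than a design fault. It does not remove the conflict, because the SAP omits the sentence that would resolve it.

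A second reply is that severe events are handled elsewhere. This also stands. A reader might infer that grade 4-5 events would go unseen, and the documents do not support that. They are estimated by grade, type and relatedness. Protocol 8.4 requires immediate medical review of unanticipated adverse device effects. Protocol 10.3.2 says: "If any grade V AEs occur during the investigation, the FDA will be notified immediately and the study halted for further accrual". None of this puts the event into the pooled rate or gives it an interval.

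Third, the counts in the last row of the table are remote. Protocol 10.3.1 expects 0 of 50, and 10.3.2 reports no grade III or IV events in over 600 patients in earlier MSOT studies. Expansion is requested only if the first 10 patients have no grade III-V event, so on the planned path all five events would fall among patients 11 to 50. All of this is correct.

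Three stronger readings should be resisted:

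- A reader might infer that passing 20% reverses a decision. At 50 patients the 20% figure describes precision, and no rule depends on it.
- A reader might extend the illustration to 45 patients, with three at grade 3 and one at grade 4-5. The early-termination rule in 10.3.1 requires three or fewer AEs and states no grade limit. Four events would not meet it, and the study would continue to 50.
- A reader might infer that this is the plan's only pooled AE rate with an interval. The same rule in 10.3.1 ties AE counts, with no grade stated, to exact upper limits at 45 patients.

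**Conclusion.** The concern holds in a narrow form. The pooled primary safety rate and its interval are written on grade 3 in two places, the stated target of estimation is grade 3 or higher, and nothing reconciles them. As written, a related, unexpected grade 4 or 5 event is left out of that rate and interval. One omitted patient moves the upper limit from 7.1% to 10.6% when no patient has a qualifying grade 3 event, and from 19.2% to 21.8% when four do. At the expected result of 0 of 50 the effect is zero.

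The textual conflict needs no assumption. The sizes rest on the assumed counts, one qualifying event per patient, and all 50 patients in the denominator. The point should be fixed because it concerns a primary analysis and costs almost nothing to correct. It does not show a failure of safety surveillance or an error in the sample size.

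**What to change.** In Protocol 10.1.1 and SAP 7.a.ii, define the numerator as the number of patients with at least one unexpected adverse event of CTCAE v5.0 grade 3 or higher that is possibly, probably or definitely related to MSOT. Name the SAP safety population as the denominator.

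Adding the higher grades resolves the conflict itself. Counting patients is a further clarification: a binomial interval needs one yes/no result per patient, and the 4 out of 50 in 10.3.1 already implies it.

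The cost is one rewritten sentence in each of two places. The sample size, the planning bounds, the interval method, the visits and the forms are unchanged.

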6.0 Study Outcomes and Study Measures

6.1 Primary Outcome

- 6.1.1 Adverse events as characterized by CTCAE v5.0 in patients that may result from MSOT imaging ($\geq 44^{\circ}\text{C}$)¹³
- 6.1.2 Measurement of skin temperature pre- and post-MSOT imaging (pre- and post-surgery 4 measurements total) with a touch thermometer as part of the safety evaluation of the MSOT device. The thermometer will be placed onto the skin until a temperature appears, about 1 minute, and the temperature will be recorded.

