8.1 Adverse Event List for MSOT

A slight, reversible reddening and temperature increase of sensitive skin. All adverse events and expected treatment effects, including mild events, will be monitored throughout the study until discharge.

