8.2 Adverse Event Characteristics

- **CTCAE term (AE description) and grade:** The descriptions and grading scales found in the revised NCI Common Terminology Criteria for Adverse Events (CTCAE) version 5.0 will be utilized for AE reporting. All appropriate treatment areas should have access to a copy of the CTCAE version 5.0. A copy of the CTCAE version 5.0 can be downloaded from the CTEP web site (<http://ctep.cancer.gov>).
- **'Expectedness':** AEs can be 'Unexpected' or 'Expected' (see Section 8.1 above) for expedited reporting purposes only.
- **Attribution** of the AE:
 - Definite – The AE **is clearly related** to the study treatment.
 - Probable – The AE **is likely related** to the study treatment.
 - Possible – The AE **may be related** to the study treatment.
 - Unlikely – The AE **is doubtfully related** to the study treatment.
 - Unrelated – The AE **is clearly NOT related** to the study treatment.

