8.6 Post-imaging Procedural Events for MSOT

The post-imaging procedural events for MSOT are those events that are expected and standard to post-imaging as for ultrasound and include slight, reversible reddening and temperature increase of sensitive skin for a duration of ≤ 24 hours post-surgery. All unexpected events shall be captured. Post-imaging procedural events that occur in increased frequency and severity over what should normally occur in the medical opinion of the investigator will be considered adverse events (AE). AEs will be reported.

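### Section 8.2 limits the expected/unexpected label to expedited reporting, yet the pooled primary safety rate counts only unexpected events, so a related grade 3 or higher erythema can be left out

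*Protocol*

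**What the plan says.** **How the label may be used.** Protocol 8.2: "AEs can be 'Unexpected' or 'Expected' (see Section 8.1 above) for expedited reporting purposes only". The list it points to, in 8.1, is: "A slight, reversible reddening and temperature increase of sensitive skin". Section 8.6 names the same two effects and adds a limit of 24 hours after surgery.

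**What the primary outcome is.** Protocol 6.1.1: "Adverse events as characterized by CTCAE v5.0 in patients that may result from MSOT imaging". It has no condition on expectedness.

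**What the pooled rate counts.** Protocol 10.1.1: "The first analysis will pool all grade 3 unexpected events that are possibly, probably or definitely related to MSOT together", with an exact 95% Clopper-Pearson interval. SAP 7.a.ii has the same text, beginning "The first analysis will pool all grade 3 unexpected events that are possibly, probably or". Protocol 10.3.1 says that the study will allow the team to "estimate the proportion of unexpected adverse events of grade 3 or higher that are possibly, probably, or definitely related to the MSOT approach".

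**What else is reported.** Protocol 10.1.1 also says: "The adverse events will be estimated by grade, type and relatedness". Skin temperature above 44°C has a separate exact interval (Protocol 10.1.1, SAP 7.b). The gate after 10 patients and the stopping rule at 45 patients (Protocol 10.3) do not mention expectedness.

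**The concern.** A label reserved for one purpose is used for another. Section 8.2 gives expectedness no role outside expedited reporting, but the three definitions of the pooled rate use it to decide which events count. The pooled rate is the figure with the confidence interval, and the sample size is justified by it.

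The filter also acts on the device's own anticipated effect. Skin reddening and skin heating are the only expected effects named, and Appendix A asks each day until discharge about erythema at grade III or higher. The one reaction that is both anticipated and actively looked for is thus the one that the filter can remove. Two careful raters could differ. One who classifies by type of event calls a grade 3 erythema expected, and it is not counted. One who reads the list in 8.1 as covering only slight reactions calls it unexpected, and it is counted. The filter can lower the rate or leave it alone; it can never raise it.

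**Working it through.** **Step 1. Where expectedness is used.**

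| Place | Expectedness applied? |
|---|---|
| Protocol 8.2, use of the label | Expedited reporting only |
| Protocol 6.1.1, primary outcome | No |
| Protocol 10.1.1, breakdown by grade, type and relatedness | No |
| Protocol 10.1.1, pooled rate | Yes |
| SAP 7.a.ii, pooled rate | Yes |
| Protocol 10.3.1, proportion to be estimated | Yes |
| Protocol 10.3.1 and 10.3.2, gate after 10 patients | No |
| Protocol 10.3.1, stop at 45 patients | No |

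Only the pooled rate carries the filter.

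**Step 2. Does any rule turn a severe listed reaction into an unexpected one?** Section 8.1 gives no CTCAE grade ceiling. Section 8.6 comes closest, in setting out when such an event counts as an AE: "Post-imaging procedural events that occur in increased frequency and severity over what should normally occur in the medical opinion of the investigator will be considered". That decides whether the event is an AE, not whether it is unexpected. The UADE definition in 8.4 does refer to severity, but it covers unanticipated device effects only. So no rule settles the question for the pooled rate.

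**Step 3. Reproduce the plan's figures.** The upper limit of a two-sided 95% Clopper-Pearson interval for x events in n patients is the 0.975 quantile of a Beta(x+1, n−x) distribution. For x = 0 it reduces to 1 − 0.025^(1/n).

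- n = 50: 0 events, 1 − 0.025^(1/50) = 7.11% (plan: 7.1%). 4 events, 19.23% (plan: less than 20%).
- n = 45: 0, 1, 2 and 3 events give 7.87%, 11.77%, 15.15% and 18.27% (plan: 7.9%, 11.7%, 15.1% and 18.3%).

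All agree within 0.1 point, so the method is the plan's own.

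**Step 4. Effect of the filter at the planned n = 50.** The documents give no rate for related grade 3 or higher skin reactions, so the counts below are assumptions. Each event is taken to be in a different patient.

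| Events counted | Rate | Upper bound | Difference from the row above |
|---|---|---|---|
| 0 | 0% | 7.11% | – |
| 1 | 2% | 10.65% | 3.54 |
| 2 | 4% | 13.71% | 3.06 |
| 3 | 6% | 16.55% | 2.84 |
| 4 | 8% | 19.23% | 2.68 |
| 5 | 10% | 21.81% | 2.58 |

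Each event labelled expected moves the reported result up one row. For example, if one related grade 3 erythema occurs and is labelled expected, the pooled result reads 0% (upper bound 7.11%) in place of 2% (10.65%).

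**The case against.** The strongest reply is that the list in 8.1 limits severity: a grade 3 reaction is hardly slight, so it would be unexpected and counted. That is the more natural reading, and it stands as a reason to say that such an event *can* be left out, not that it *will* be. The plan does not state this rule for AEs, however. If it is what the sponsor intends, every grade 3 or higher reaction of the named types is unexpected anyway. The word then removes none of them, and deleting it loses nothing.

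Other parts of the reply also stand. An event left out of the pooled rate is not lost from the safety report, because the breakdown by grade, type and relatedness is unfiltered. Skin temperature above 44°C has its own interval, so erythema is the clear example and skin heating is not. The gate after 10 patients counts events whatever their label. The sponsor expects 0 of 50, and then the word makes no difference.

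Two stronger inferences are tempting, and the documents support neither.

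- *At 45 patients, relabelling one of four events moves the upper bound from 21.2% to 18.3% and so turns a failure into a pass.* The stop at 45 requires 3 or fewer AEs and has no expectedness filter. With four AEs the trial goes on to 50, where 4 of 50 gives 19.23% if no further event occurs. Nor is 20% a pass/fail mark for the primary result: 10.3.1 uses it to describe precision and to justify the early stop.
- *The investigator decides, after the event, what counts.* No section assigns the expectedness label to the investigator. Section 8.0 has the center assess AEs, including whether they are unanticipated. SAP 7.a.i gives the investigator severity grading, and 8.6 leaves to the investigator's opinion whether a procedural event becomes an AE.

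**Conclusion.** The inconsistency is real and should be fixed. Section 8.2 and the three definitions of the pooled numerator cannot all stand, and the filter leaves it open whether a related grade 3 or higher erythema enters the main safety estimate. At n = 50, each event left out lowers the exact upper bound by about 2.6 to 3.5 points, over the range from 0 to 5 events. This size rests on assumed event counts, one event per patient, and a rater who classifies by type and not by severity. With no such event the result is unchanged. The fault is confined to the pooled rate and its interval. It does not mean that the study fails to collect or report these events.

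**What to change.** Delete the word unexpected from the pooled numerator in Protocol 10.1.1, Protocol 10.3.1 and SAP 7.a.ii, so that it counts all events of the stated grade that are possibly, probably or definitely related to MSOT. Keep expectedness for expedited reporting, as 8.2 says. If the sponsor wants the split, report the unexpected subset as a second line.

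A statement that any grade 3 or higher skin reaction counts as unexpected would also settle the classification, but it would leave the conflict with 8.2 in place.

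In the same edit, reconcile the grade: 10.1.1 and SAP 7.a.ii say grade 3, while 10.3.1 says grade 3 or higher. That is a separate inconsistency.

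The cost is one word in three places, with no new data and no change in sample size. The reported rate can only stay the same or rise.
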